6.2.2.5 Karyotyping

To determine the chromosome complement of the cells we will carry out chromosomal karyotyping using a commercial protocol or an outsourced commercial karyotyping service.

6.2.2.6 Immunocytochemistry

We will use indirect immunocytochemistry (ICC) to characterise iPSC and cardiomyocyte cell lines at the protein level. This method will allow us to generate data that will confirm the simultaneous expression and cellular location of key pluripotent stem cell markers and cardiac-specific markers such as Troponin-T. The stained cells will be viewed using a fluorescence microscope and the images will be captured using a digital camera. Captured images will be interpreted and analysed with the aid of an appropriate imaging software, such as Adobe Photoshop, and data may be manipulated to include the addition of scale bars, contrast adjustment and image overlays. Data manipulation will not affect the result of the experiments in any way. Our interpretations of the data will be validated with the use of positive and negative staining controls and imaging parameters for the controls will be the same as those applied to the test dataset. In addition to obtaining data on protein expression levels, the cardiomyocyte differentiation efficiency will also be assessed by ICC. A select number of images (<5) will be captured at random and the number of cardiac TroponinT- positive cells will be divided by the total cell count. Cells will be counterstained with a nucleic acid stain (DAPI) to achieve this.

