3.6 SAMPLING

3.6.1 Size of sample

The maximum sample size for this pilot study at this stage will be 12 participants in total across all experimental groups (Figure 1). When selecting a sample size for this study we considered several factors including the nature of the study (i.e. a pilot study) and the financial feasibility of achieving our research aims at this stage. As this is a pilot study, we want to generate preliminary data that can support further funding applications that build on scientific evidence and eventually allow for larger sample sizes whilst still working realistically within the constraints of the study. Our approach is therefore to focus our efforts on obtaining a carefully planned smaller sample size which adequately represents significant aspects of the wider study population. This sample size is large enough to sufficiently address the primary research aims at the current stage and will provide valuable preliminary data to plan larger subsequent studies which will further address the overarching research questions.

Version 2.21. Date: 1517/095/2022; IRAS:

Page 23 of 44

Formatted: Indent: Left: 0.35 cm

[figure not shown]

Figure 1. Cancer patients with early-onset chronic cardiotoxicity and late-onset chronic cardiotoxicity will be recruited. Non-cardiotoxic patients will be matched to the cardiotoxic patients on tumour type, treatment regime and approximate age. For late-onset chronic cardiotoxic patients, noncardiotoxic patients will be recruited who have previously received the same treatment regime and not developed cardiotoxicity at the same point.

Version 2.21. Date: 1517/095/2022; IRAS:

Page 24 of 44

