6.2.2.3 Microscopy

Brightfield microscopy will be used to analyse cellular reprogramming and differentiation efficiency as well as to assess the regular progress and overall health of the cells whilst in culture. Reprogramming efficiency will be assessed by microscopy in two ways – firstly, following transduction/transfection, all newly generated iPSC colonies will be counted and divided by the number of input cells used for reprogramming. Secondly, the number of iPSC colonies that survive following picking will be divided by the number of colonies that are selected for picking. The cardiomyocyte differentiation efficiency will be determined by dividing the number of observed beating areas by the total number of iPSC colonies that are used for differentiation.

Overall cell health will be assessed through regularly examining the morphology of the cells. Reprogrammed iPSC colonies will be examined for typical features indicative of good health such as dense, flat, rounded colony formation with even colouring and a high nucleus-to-cytoplasm ratio.

Microscope data on cell morphology, reprogramming efficiency and differentiation efficiency will be collected using and Invitrogen EVOS XL Core imaging system and analysed using an appropriate imaging software programme.

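### The troponin-T-positive fraction is capped at four images, with no minimum number of images or cells and no stated sampling unit

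*Protocol*

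**What the plan says.** Section 6.2.2.6 (Immunocytochemistry) states that "the cardiomyocyte differentiation efficiency will also be assessed by ICC". The sampling rule is "A select number of images (<5) will be captured at random", and the estimator is that "the number of cardiac TroponinT- positive cells will be divided by the total cell count", with a DAPI nuclear counterstain supplying the total.

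The section gives no minimum number of images or cells and does not name the unit to which the images belong. It also gives no expected fraction, between-image spread, target precision or acceptance threshold.

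Section 6.2.2.3 (Microscopy) has a second efficiency measure: "The cardiomyocyte differentiation efficiency will be determined by dividing the number of observed beating areas by the total number of iPSC colonies" used for differentiation. Section 3.6.1 sets the scale of the work: "The maximum sample size for this pilot study at this stage will be 12 participants in total across all experimental groups".

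**The concern.** A sampling rule for an estimate normally guarantees a minimum amount of information. This one limits the maximum and guarantees nothing: the fewest images that satisfy it is one, and a laboratory that took more for better precision would be outside the protocol.

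The fraction matters because it is the only figure in the protocol that says what share of the cells in a culture are cardiomyocytes. Beating areas per colony is a ratio of a different kind and does not give a cell fraction. Section 6.2.2.7 (Mass Spectrometry) then compares whole-proteome data between cardiotoxicity and non-cardiotoxicity samples by principal components and a two-tailed t test, and the protocol describes no purification step before that. If cultures from the two groups differed in cardiomyocyte content, the difference could appear as differential protein expression. The troponin-T-positive fraction is the natural place to see it, provided it is measured well enough.

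**Working it through.** The protocol states no precision for this measure, so there is no figure of its own to reproduce. The check asks what the permitted numbers of images could deliver.

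**Inputs from the protocol:** at most four images and no minimum (Section 6.2.2.6); at most 12 donors (Section 3.6.1).

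**Input assumed:** the between-field standard deviation (SD) of the positive fraction. The documents do not give it; 5, 10 and 20 percentage points are shown.

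**Formula:** approximate 95% half-width on the mean of k field fractions = t(0.975, k−1) × SD / √k.

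- Four fields: t = 3.182 and √4 = 2. SD 10 gives 3.182 × 10 / 2 = 15.9; SD 20 gives 3.182 × 20 / 2 = 31.8.
- Three fields: t = 4.303 and √3 = 1.732. SD 10 gives 4.303 × 10 / 1.732 = 24.8.
- Ten fields: t = 2.262 and √10 = 3.162. SD 10 gives 2.262 × 10 / 3.162 = 7.2.

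| Fields | SD 5 | SD 10 | SD 20 |
|---|---|---|---|
| 1 | none | none | none |
| 2 | ±44.9 | ±89.8 | ±179.7 |
| 3 | ±12.4 | ±24.8 | ±49.7 |
| 4 (the maximum allowed) | ±8.0 | ±15.9 | ±31.8 |
| 10 | ±3.6 | ±7.2 | ±14.3 |

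All half-widths are in percentage points. At SD 10 and 20, two fields are uninformative. With one field the between-field variation cannot be estimated at all.

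**How far the answer depends on the assumption.** With four fields, an SD of 2 gives ±3.2 and an SD of 25 gives ±39.8. Using the normal quantile in place of t, four fields give ±9.8 at SD 10 and ±19.6 at SD 20.

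**If only the cell count mattered.** Pool four fields of 100 cells each (an assumed number) with no variation between fields beyond counting. The half-width is 1.96 × √(p(1−p)/400), which is ±4.9 at p = 0.5, ±4.5 at p = 0.7 and ±2.9 at p = 0.9.

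**What the SDs mean.** At p = 0.5 and 100 cells per field, counting alone gives a field SD of √(0.25/100) = 5.0 points. At that cell count, SD 5 therefore means evenly spread cells. If cells in the same field are correlated at ρ, the field SD is √(p(1−p)(1+99ρ)/100). That is 12.2 points at ρ = 0.05, 16.5 at ρ = 0.1 and 22.8 at ρ = 0.2. An SD of 10 to 20 thus corresponds to modest clustering, but the protocol does not say how much to expect.

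**The case against.** The strongest reply is that this is a descriptive characterisation assay in a small pilot, that field counts can sit in a laboratory procedure, and that any precision figure depends on an SD the documents do not supply. The last part stands: a reader might infer that the cardiomyocyte content of each line is known only to within 16 to 32 points, but that range needs exactly four fields and an assumed SD of 10 to 20. With more uniform cultures four fields could do noticeably better. Nor can the figures be stated per line, because the unit is not given; if the limit applies per well or per differentiation, a line could have more than four images. The laboratory-procedure argument is weaker, because the protocol does fix a number and fixes it as a ceiling.

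The interval also does not match the estimator exactly. The protocol pools cells, while the calculation averages field fractions. The two are close when fields hold similar numbers of cells, but the half-widths are approximate, and the widest show a symmetric interval breaking down on a 0 to 100% scale.

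Three stronger readings are tempting and not supported:

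- **That the sampling wording contradicts itself, being both selective and random.** The first term describes how many images are taken and the second which fields. Section 6.2.2.7 uses the same idiom for a count of proteins.
- **That a poor line cannot be told from a good one.** The protocol sets no threshold and plans no comparison of lines on this fraction. Even at ±16 points, lines at 30% and 90% would be clearly separated.
- **That the fraction is a purity gate for proteomics or part of the primary outcome.** Section 6.2.2.6 calls it differentiation efficiency. Section 3.3 does not name it, Section 2.1.1 validates cardiomyocyte lines by several methods together, and Section 6.2.2.3 supplies the second efficiency measure.

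**Conclusion.** The drafting defect is certain: a maximum has been fixed where a minimum is needed, and the number of cells and the sampling unit are left open. Its numerical size is conditional on the unknown between-field SD. At the permitted maximum of four, the half-width runs from about 8 points (SD 5) to about 32 (SD 20), and fewer images make it worse.

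The consequence is limited but real. An imprecise fraction may fail to show a difference in cardiomyocyte content between the groups whose proteomes are compared. Nothing in the documents shows that such a difference exists. This is a cheap improvement, not a flaw that undermines the study.

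**What to change.** In Section 6.2.2.6, replace the upper limit with a minimum per line and differentiation, for example at least ten fields, placed randomly or systematically, over at least two wells, together with a minimum total cell count. Keep the pooled ratio of positive to total cells, and report it with a standard error that treats the field (or well) as the sampling unit.

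Ten fields and two wells are illustrative, since the protocol gives no precision target from which to derive them. Two wells will reveal gross disagreement, but if wells differ materially, the ten-field half-widths above will be too narrow.

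The cost is modest extra imaging and counting for at most 12 donors, with methods already planned, and no further blood samples or patient contact.

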6.2.2.7 Mass Spectrometry (MS)

Version 2.24. Date: 1547/095/2022; IRAS:

Page **31** of **44**

To generate quantitative data on the whole proteome of doxorubicin-treated cardiomyocytes, cardiomyocytes from all experimental groups will be subjected to iTRAQ-based MS. To determine whether protein expression is similar between cardiotoxicity and non-cardiotoxicity samples, the data will be subjected to principal component analysis to analyse the variance across the sample sets and identify whether there is a distinction between them based on protein expression. A two-tailed *t* test will be carried out using the R computational environment to determine the statistical significance of differences in protein expression between cardiotoxicity and non-cardiotoxicity samples

To validate the iTRAQ-MS data, we will use Western blot analysis to verify the differential protein expression of a select number of identified proteins. The identity of the target proteins will be confirmed by comparison to a molecular weight marker (for size) and a positive control if possible (for size and signal). A loading control will be used to allow us to normalise the data and compare the expression levels between the target proteins. The data produced will be interpreted using imaging software, such as ImageJ, and a semi-quantitative comparison will be made of the signals generated between protein bands.

Following validation, proteins which are found to have a statistically significant higher or lower level of expression by MS in the control samples will be explored further using computational enrichment analysis to identify functional pathways involved in cardiotoxicity.

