2.1 AIMS AND OBJECTIVES

2.1.1 Aim 1

To generate cardiomyocytes from patient-derived iPSCs.

Objectives

To achieve this, we will:

Version 2.24. Date: 1547/095/2022; IRAS:

Page 19 of 44

- Separate peripheral blood mononuclear cells (PBMCs) from patient blood samples.
- Reprogram PBMCs into iPSCs cells using the four Yamanaka transcription factors which will be introduced via Sendai-virus transduction or electroporation.
- Characterise and validate iPSC lines using microscopy, immunocytochemistry, and polymerase chain reaction (PCR).
- Develop reprogrammed iPSCs into patient-specific cardiomyocytes.
- Characterise and validate cardiomyocyte lines using microscopy, immunocytochemistry, PCR, and electrophysiology.

2.1.2 Aim 2

To characterise the mechanistic differences between patients with and without anthracycline-induced cardiotoxicity.

Objectives:

To achieve this, we will:

- Conduct proteomic profiling studies in cardiomyocytes generated from test subjects to detect short and long-term changes in protein expression levels.
- Characterise the electrical activity and calcium homeostasis of cardiomyocytes.
- Measure ionic currents, along with cardiac action potential to investigate morphological and pathophysiological changes in whole cell electrical signalling.
- Measure intracellular Ca²⁺ changes, intracellular ATP, mitochondrial function, and membrane potential.
- Analyse differences in mechanical beating behaviour between cardiomyocytes.

2.1.3 Aim 3

To Identify and characterise novel candidate biomarkers.

Objectives

To achieve this, we will:

- Use iPSCs to characterise biomarkers that can be readily validated within cells and secreted into media.
- Compare these to biomarkers found in blood obtained from patients.
- Compare the findings to the current method of detection of biomarkers at the participating hospital site (LHCH) to potentially identify new biomarkers through blood-based proteomics.

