3.3 OUTCOME

Our primary outcome for this study is to generate iPSC-derived cardiomyocytes that are reproducible, amenable to experimental analysis, and that recapitulate the phenotype of the donor at the molecular and cellular level. This will not only allow us to begin addressing the research questions set out in this study of being able to better understand chemotherapy-induced cardiotoxicity, but will also enable us to use the technology to investigate other cardiac conditions and congenital defects.

Secondary outcomes include:

- Identifying a doxorubicin-specific signature in the cells derived from our cardiotoxicity subjects
 which signifies a distinct biological process that is absent in the control group. This would allow us
 a potentially significant insight into the mechanistic effects of doxorubicin-induced cardiotoxicity
 at a cellular and molecular level.
- Identifying candidate biomarkers that are of a functional relevance to doxorubicin-induced cardiotoxicity. Novel biomarker discovery could potentially offer an enhanced alternative to the current standard of risk stratification and cardiotoxicity detection in the clinic.
- Obtaining data that will support further investigations into different areas of future research such as the role of candidate biomarkers that could predict anthracycline-induced cardiotoxicity in other cancers and what their relationships are to cumulative drug dosing strategies for example.

These outcomes could eventually enable clinicians to better predict which patients will develop cardiotoxicity and how their care can be more appropriately managed. The research will deepen the understanding of doxorubicin-induced cardiotoxicity for health care professionals and service providers for integrated care. It will also assist in providing a better understanding of the options available for supporting chemotherapy patients at various stages of their care both during and following the completion of their treatment. It has the potential to improve the wellbeing and lives of patients as well as to improve how primary and secondary care services work together. The study will develop high quality data that will be disseminated with researchers, service users and health care professionals to create more effective practices in care.

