4.2.2 Non-cardiotoxicity Cohort

- Over 16 years of age at the time of consent.
- Capable of providing informed consent as determined by the consenting clinician.
- Receiving doxorubicin chemotherapy treatment at the time of consent or previously received doxorubicin chemotherapy treatment prior to consent.
- Normal left ventricular systolic function at the time of consent secondary to receiving doxorubicin chemotherapy treatment as determined by the clinical team.

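### The proteomic comparison is between donors only, so it cannot show that a difference is specific to doxorubicin or that it is a change

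*Protocol*

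**What the plan says.** Section 6.2.2.7 sets out the proteomics: "To generate quantitative data on the whole proteome of doxorubicin-treated cardiomyocytes, cardiomyocytes from all experimental groups will be subjected to iTRAQ-based MS". Principal component analysis is followed by a two-tailed t test of "differences in protein expression between cardiotoxicity and non-cardiotoxicity samples". Proteins with a "statistically significant higher or lower level of expression by MS in the control samples" then go forward to enrichment analysis, to find pathways involved in cardiotoxicity. No other proteomic contrast is given.

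Section 3.3 lists as its first secondary outcome "Identifying a doxorubicin-specific signature in the cells derived from our cardiotoxicity subjects", marking a biological process that the control group lacks. Aim 2 in section 2.1.2 plans proteomic profiling "to detect short and long-term changes in protein expression levels".

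The experimental groups are groups of people. Section 3.6.1 says that the maximum sample size "will be 12 participants in total across all experimental groups (Figure 1"), and the figure caption explains: "Cancer patients with early-onset chronic cardiotoxicity and late-onset chronic cardiotoxicity will be recruited", with matched non-cardiotoxic patients alongside. The controls are not drug-naive. Section 4.2.2 requires past or current doxorubicin treatment and "Normal left ventricular systolic function at the time of consent secondary to receiving doxorubicin chemotherapy treatment as determined by the clinical team".

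**The concern.** To call a signature specific to doxorubicin, one must know what the same cells look like without the drug, or at least that the response to the drug differs between the groups. A comparison of case lines with control lines under one common condition gives neither. Donors differ in their proteomes for reasons unrelated to doxorubicin, and matching on tumour type, age and regime (section 3.5.1) does not remove such differences between lines. The word *changes* in Aim 2 has the same problem, because section 6.2.2.7 names no starting point or time points to change from.

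At stake is the label on the result. A constitutional donor difference could be reported as a drug effect, passed to pathway analysis under that label, and then used to plan the larger studies that this pilot is meant to support.

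**Working it through.** The protocol gives no effect size, SD, significance level or power for this comparison, and section 3.6.1 justifies the maximum of 12 by pilot status and finance. There is no stated figure to reproduce. The question is what the design can estimate.

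**Step 1: the two readings of doxorubicin-treated cardiomyocytes.** Write the expression of one protein as

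y = μ + β·(case) + δ·(exposed) + θ·(case × exposed) + donor effect + residual,

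where β is the constitutional difference between case and control donors, δ the common effect of doxorubicin on the cells, and θ the difference in response between the groups. A drug-specific signature is a statement about θ.

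- If the phrase refers to the donors, the cultured cells derived from reprogrammed blood cells are not exposed, and exposed = 0 throughout. Cases minus controls = β.
- If the cells are dosed in vitro, all of them are, and exposed = 1 throughout. Cases minus controls = β + θ.

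On neither reading is θ estimable. The design matrix for the second reading has 4 columns and rank 2, because exposure coincides with the intercept and the interaction coincides with group. For the first reading the last two columns are zero, so the rank is again 2. With each line cultured both ways (12 × 2 = 24 samples) the rank is 4 of 4. This result needs no assumed effect size or variance.

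**Step 2: what the planned test would show.** The assumptions, none from the protocol, are 6 v 6 donors, one line each, an unpaired t test at two-sided 5%, between-donor SD 1, within-line SD 0.5, a common exposure effect of 1.0, all cells exposed, and 100,000 runs.

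| Truth (β, θ) | Planned contrast: mean, rejection | Within-line change: mean, rejection |
|---|---|---|
| 0, 0 | 0.00, 5% | 0.00, 5% |
| 1.5, 0 | 1.50, 55% | 0.00, 5% |
| 0, 1.5 | 1.50, 55% | 1.50, 91% |
| 1.5, −1.5 | 0.00, 5% | −1.50, 91% |

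Rows two and three look identical to the planned test. Row four shows that opposing effects can hide a real differential response.

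**Step 3: sensitivity.** For within-line SD from 0.25 to 1.0, rows two and three stay indistinguishable, with rejection falling from about 62% to 38% in both. The within-line change stays at 5% in row two. In row three it rejects in 100%, 91% and 38% of runs at SD 0.25, 0.5 and 1.0. The variance of a change is 2s² against 1 + s² for a single exposed measurement, so the change is the more precise quantity only when s is below 1.

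**Step 4: search for an unexposed comparator.** Sections 6.2.2.1 to 6.2.2.8 describe no in-vitro doxorubicin step, no vehicle culture of the same line and no before-and-after MS sample. The control samples of 6.2.2.7 read as the non-cardiotoxicity donors. The Western blot controls are for loading and, if possible, for size and signal. The controls collected daily in 6.2.2.8 belong to electrophysiology and imaging, and neither their line nor their exposure is defined. The only challenge to the cells named there is simulated ischaemia.

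**The case against.** A reader might infer that the study cannot answer its main mechanistic question. The protocol does not support that. Sections 1.2 and 3.1, and the opening of Aim 2, ask how cells from patients with cardiotoxicity differ from cells of matched patients without it, and a between-donor contrast addresses this. Section 1.2 also looks for baseline factors that stratify risk. As the controls received the same drug, a constitutional difference may itself be a susceptibility factor, which is a result the study wants. Section 2 leaves the overarching questions to larger studies. All of this stands, and it limits the point to one secondary outcome and one objective.

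It is also tempting to read the 55% as an error rate. In those runs the groups really do differ by 1.5 SD, so the test is right to reject. The mistake comes afterwards, if the difference is attributed to the drug.

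Finally, silence is weak evidence about the laboratory plan. The flow chart and Figure 1 are not visible, and the methods do not describe cardiomyocyte differentiation either, although the study depends on it. An unexposed culture may be intended. But the text and the caption describe Figure 1 as groups of participants, and the one contrast that 6.2.2.7 fixes would not use such a culture. Exposure of the cultures is a matter of experimental design and would not normally be left to an analysis plan.

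**Conclusion.** The concern holds in a limited form. As written, the comparison in 6.2.2.7 can show that cardiomyocytes from donors with and without cardiotoxicity differ. It cannot show that the difference is specific to doxorubicin (section 3.3) or that it is a short-term or long-term change (Aim 2). The primary outcome, generating usable cardiomyocytes, and the general case-control comparison are unaffected.

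This conclusion rests on the structure of the design and on the visible text. The simulated rates rest on an assumed 6 v 6 split and assumed SDs. They show only that a donor difference of that size would often be detected and could then be given the wrong cause.

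**What to change.** State in 6.2.2.7 whether the cardiomyocytes are exposed to doxorubicin in vitro. Then take one of two routes.

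- **If they are exposed and resources allow:** culture each line with and without exposure, handled identically in both groups, and compare the within-line change (exposed minus unexposed) between the groups. Name the time points if Aim 2 is to keep *changes*. The lines are cryopreserved (6.2.2.2), so no new participants are needed. The cost is at least double the MS samples: 12 × 2 = 24 at the maximum sample size, and 12 × 2 × 2 = 48 with two time points. The extra culture work would fall on the single research assistant who carries out all experimental methods (6.2.2), in a study already limited by funds.
- **Otherwise:** reword the outcome in 3.3 as *proteomic differences between cardiomyocytes from donors with and without cardiotoxicity*, delete *doxorubicin-specific*, and replace *changes* in Aim 2 with *differences*. This wording is correct whether or not the cells are dosed, and it costs nothing.

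### The only proteomic contrast in 6.2.2.7 compares cases with controls in one condition, so it can show a case-control protein difference but cannot support the doxorubicin-specific signature named in 3.3

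*Protocol*

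**What the plan says.** **Outcome.** Section 3.3 lists as its first secondary outcome "Identifying a doxorubicin-specific signature in the cells derived from our cardiotoxicity subjects", and describes this signature as one "which signifies a distinct biological process that is absent in the control group". It is expected to give "a potentially significant insight into the mechanistic effects of doxorubicin-induced cardiotoxicity".

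**Material.** Section 6.2.2.7 sets out the proteomics: "To generate quantitative data on the whole proteome of doxorubicin-treated cardiomyocytes, cardiomyocytes from all experimental groups will be subjected to iTRAQ-based MS". The experimental groups are groups of participants, not culture conditions: section 3.6.1 sets the maximum at "12 participants in total across all experimental groups (Figure 1"), and the caption of that figure describes patient groups only.

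**Contrast.** The stated purpose in 6.2.2.7 is "To determine whether protein expression is similar between cardiotoxicity and non-cardiotoxicity samples". The methods are principal component analysis and then a significance test: "A two-tailed *t* test will be carried out using the R computational environment". Proteins that differ significantly go on, after validation, to pathway enrichment.

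**Controls.** The control donors also had the drug. Section 4.2.2 requires "Receiving doxorubicin chemotherapy treatment at the time of consent or previously received doxorubicin chemotherapy treatment prior to consent", and 4.2.1 sets the same condition for cases. The controls mentioned within 6.2.2.7 belong to the Western blots. The daily control data sets in 6.2.2.8 belong to electrophysiology and imaging and are not defined as untreated cultures of the same lines.

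**The concern.** A claim that a protein pattern is specific to doxorubicin needs a comparison in which the drug is present on one side and absent on the other. The protocol describes none for the proteomics. The phrase about doxorubicin-treated cardiomyocytes can be read in two ways, because no in vitro exposure step is described anywhere else:

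- If the cells are dosed in the dish, the group difference mixes what the lines were like beforehand with how they responded.
- If the phrase means cells grown from treated patients, no drug response is measured at all.

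The objective under Aim 2 (2.1.2) speaks of short-term and long-term changes in expression, but gives no reference state from which a change would be measured.

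At stake is how the result is labelled. Followed as written, the plan would take an ordinary case-control difference, send it to pathway analysis, and report it against an outcome that calls it drug-specific. The pilot is meant to support further funding applications (3.6.1), so the label would carry into later work.

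**Working it through.** The protocol gives no alpha, SD, effect size or power for this contrast, and justifies the 12 participants by pilot status and finance. There is no planned figure to reproduce. The question is what the stated comparison can identify.

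**1. Model.** For one protein, let μ be the control mean without drug, *b* the pre-existing case-control difference, τ the drug effect in controls, and *g* the extra drug effect in cases. The drug-specific claim is about *g*.

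**2. Reading A: cells dosed in vitro, exposed cultures only.**
- Case mean = μ + b + τ + g
- Control mean = μ + τ
- Difference = b + g

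Two means for four parameters: the design matrix has rank 2 of 4. Neither *g* nor τ can be estimated separately.

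**3. Reading B: cells from treated donors, not dosed.** Neither τ nor *g*, the in vitro drug effects, enters the data. The comparison estimates *b*.

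**4. With an unexposed culture of each line.** Two further means appear, μ + b for cases and μ for controls. The rank becomes 4 of 4, and *g* is (case exposed − case unexposed) − (control exposed − control unexposed).

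**5. Illustration by simulation.** 40,000 runs; assumed 6 v 6 lines, two-sided alpha 0.05, line SD 0.8 and culture SD 0.6 (total √(0.64 + 0.36) = 1), τ = 1. Entries are mean difference and rejection rate.

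| b | g | Exposed cultures only | Within-line change |
|---|---|---|---|
| 2 | 0 | 2.0; 87.9% | 0.0; 5.1% |
| 0 | 2 | 2.0; 87.9% | 2.0; 95.7% |
| 1 | 1 | 2.01; 87.7% | 1.0; 45.2% |
| 2 | −2 | 0.0; 4.9% | −2.0; 95.7% |

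The first two rows differ entirely in mechanism and look the same to the planned test. The last row is a real response difference that the planned test misses.

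**6. Power of the planned test for a baseline-only shift.** Noncentral *t*, 10 df, noncentrality d × √(6 × 6 / 12) = d√3. For d = 0.5, 1.0, 1.5 and 2.0 SD: 12%, 35%, 65% and 88%. With an 8 v 4 split, d = 1.0, 1.5 and 2.0 give 32%, 60% and 84%.

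**7. Precision of the added contrast.** If exposed and unexposed values of a line have equal variance and correlation *r*, the variance of the change relative to a single value is 2(1 − r). The standard error ratio is √[2(1 − r)]: 1.00 at r = 0.5, 0.77 at 0.7, 0.63 at 0.8, 0.45 at 0.9. Below 0.5 the change contrast is the less precise of the two.

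**8. The word absent.** A *t* test asks whether two means are equal. Rejection shows a difference in level. It does not show that the process is missing in controls, and no other step in 6.2.2.7 tests for that.

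**The case against.** The strongest reply is that a pre-existing difference between donors' lines is something the study wants to find. Section 1.2 speaks of stratifying baseline risk on histological and genetic factors, and section 2 asks how patients who develop cardiotoxicity differ and whether they can be recognised before symptoms. The direct comparison answers that, and controls are matched on tumour type, age and treatment regime (3.5.1). This stands: the comparison should be kept. It does not make the result drug-specific.

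Four stronger readings are tempting but not supported:

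- **That the study has no untreated culture.** The protocol specifies none. Figure 1 and the flow chart are not shown, and a laboratory procedure could include one.
- **That clone or culture variation will appear as a signature.** With the line as the unit, random variation of this kind goes into the error term. Only a systematic group shift moves the contrast.
- **That 12% to 88% is a false-positive rate.** It is ordinary power to detect a real group difference of an assumed size. The error would lie in calling that difference drug-specific.
- **That the secondary outcome is out of reach altogether.** Section 3.3 does not tie the signature to mass spectrometry alone, and 2.1.2 and 6.2.2.8 list other assays. None of them names an unexposed reference either, but the point made here concerns the proteomic analysis.

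Pilot status excuses low power and ambitious wording to a degree. It does not change what a one-condition comparison estimates.

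**Conclusion.** The point holds in this form: as specified, the proteomic comparison validly estimates a case-control protein difference, and on that analysis it cannot support a doxorubicin-specific signature or a process absent in controls. This is so under either reading of the phrase about treated cardiomyocytes.

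The size is structural: b + g is estimated where *g* is claimed. That does not depend on the split, alpha, SDs or effect sizes, all of which are assumed in the illustration. The percentages show only how the confounding would look in a study of this size.

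It should be corrected, because a named secondary outcome and the analysis behind it do not match, and the minimum correction is wording.

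**What to change.** Reconcile 6.2.2.7 with 3.3 by stating whether the cardiomyocytes are exposed to doxorubicin in vitro and against what reference. Exposure conditions are for the sponsor to set; none is proposed here.

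- **If they are exposed:** keep the direct case-control comparison. Add a matched unexposed (vehicle) culture of each line, and name the case-control difference in within-line change (log2 exposed minus log2 unexposed, line as the unit) as the contrast behind any drug-specific claim. Even then, 3.3 should speak of a difference in response, not of a process being absent.
- **If they are not exposed, or the extra samples are not feasible:** remove the drug-specific and absent-in-controls wording from 3.3 and report a case-control protein difference.

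**Cost.** The first option needs up to 12 more mass spectrometry samples per time point, and the short-term and long-term aim in 2.1.2 could multiply that. No new donors are needed. The documents do not give iTRAQ capacity, reprogramming success varies (3.5.1), and one research assistant does all the experiments (6.2.2), so feasibility must be checked. The added contrast is also less precise than the direct one if the within-line correlation is below 0.5. The second option is a text change only.
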